**Version 5**  
**August 3, 2023**

## Summary of Protocol Changes

Version 4.1, 1/17/22

- Changed the types of blood tubes for blood sample collection (to make laboratory processing easier). Blood draw volumes remain the same.

Version 4, 5/18/21

- Changed age of eligibility from 8-17 years to 6 up to 21 years of age
- Expanded definition of “exacerbation” for eligibility purposes
- Added option for a single study visit with telephone/email follow-ups and review of medical records
- For participants who consent to the 48 week follow-up, added option for visits 3, 4 and 5 to be completed by telephone

Version 5, 8/3/23

[figure not shown]
- Added two additional specific aims and their analysis plans to the study protocol that will be funded through an Administrative Supplement to the parent grant.

## A. Background

Asthma symptom control is suboptimal in the majority of children in the United States, despite widespread availability of asthma controller medications and standardized treatment guidelines. While deaths from asthma have declined, 53.7% of children with asthma continue to experience an exacerbation each year and the associated public health burden is substantial. Indeed, national surveillance data in children highlight disturbing trends of decreased primary care visits for asthma, increased emergency department visits for asthma exacerbations, and rising asthma costs estimated at \$82 billion annually. School absenteeism and decreased productivity in working parents are also consequences of childhood asthma that negatively impact affected children and their families.

While the factors responsible for poor asthma symptom control are complex and include limited access to care, poor adherence to preventative asthma medications and exposures to environmental allergens and irritants such as tobacco smoke, it is also recognized that children with exacerbation-prone asthma are a heterogeneous group with differing clinical outcomes and longitudinal disease trajectories.

** Symptoms (defined as subjective sensations)** can also be quite varied within and among affected children. Whereas some children have persistent, troublesome respiratory symptoms, others have respiratory

**Figure 1.** Symptom domains (large circles) and potential symptom clustering (overlap areas) in children with exacerbation-prone asthma.

symptoms only with upper respiratory infections. Mental health symptoms and social health symptoms have been inadequately characterized in this population, but some children with asthma also report depression and anxiety and impaired family functioning and relationships that may further worsen asthma outcomes. However, prior studies are limited by a narrow focus on individual symptoms in isolation. To date, there has been no attempt to identify **symptom clusters (defined as two or more concurrent symptoms independent of other clusters) (Figure 1)** in children with exacerbation-prone asthma.

Poor understanding of symptom clusters is a major shortcoming in asthma symptom science. In other chronic disorders such as cancer, compared with a single symptom, symptom clusters of pain, fatigue, sleep disturbance and mood disturbance significantly worsen patient-reported outcomes of functional status and quality of life. There is also emerging evidence that interventions for one symptom within a cluster (i.e., cognitive-behavioral therapy for pain) reduce the severity of other symptoms within that cluster (i.e., fatigue and sleep disturbance). Because children with exacerbation-prone asthma rarely report a single symptom, greater knowledge of the assessment (and ultimately management) of symptom clusters in these children has the potential to significantly improve individualized treatment and clinical outcomes.

## **B. Study hypothesis/aims**

We propose a 48-week cohort study (N=173) to test the overarching hypothesis that symptom clusters and their associated inflammatory and metabolic pathways predict corticosteroid treatment responsiveness (primary objective outcome) and quality of life (patient-reported secondary outcome) in children 6 up to 21 years with exacerbation-prone asthma.

### **Aim 1. Identify and phenotype symptom clusters and assess their temporal trajectories in children with exacerbation-prone asthma.**

Hypotheses: A cluster of children with the poorest physical, mental, and social health symptoms will be identified by latent class analysis; this cluster will have stable symptom presentations over time.

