## U. Statistical analysis plan

### Plan for parent R01 study (aims 1-3)

Latent transition analysis (**LTA**) is a cluster-based model that allows for integration of repeated data. Discrete latent classes of individuals are identified based on their shared characteristics across a set of observed categorical variables and models are allowed to change over time between classes. Parameters estimated in LTA include class membership probabilities and item response probabilities, which are used to characterize the group structures. LTA also produces a transition probability matrix, estimating probabilities of membership in the same group at each time point (entries along the diagonal) and probabilities of transitioning to a different group over time (entries off the diagonal). Parameters are combined mathematically into a likelihood function, and the set that maximizes the likelihood function determines the membership of each individual in one of the latent classes.

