Because LTA is aimed at characterizing transition over time, it requires variability in all variables. Therefore, we will perform LTA with patient-reported symptoms (global, mental, social and physical health categories) and measures of asthma disease activity (ACQ, ACT, lung function, exhaled nitric oxide, blood eosinophils) measured at baseline and visits 3, 4 and 5 (**see Appendix 1**). Age, sex, race, ethnicity, socioeconomic status, medications, exposures and allergic sensitization measured at the baseline visit will be considered stable and treated as covariates in the LTA model. All participants will be included in the analysis since missing data for the variables are handled in the procedure, with data assumed to be missing completely at random. The test of the null hypothesis that data are missing completely at random (Missing Completely At Random test in the SAS LTA procedure) will be evaluated; if non-significant, missingness does not affect the interpretation of the results. The number of classes will be statistically determined using the Bayesian information criterion (**BIC**) and class prevalence if BICs are of a similar magnitude, to avoid a solution leading to low prevalent groups (<5%). To assess the stability of the group structure, goodness of fit of the “constrained” LTA model in which identical item-response probabilities across time are estimated (i.e., the same cluster structure is forced into multiple time points) will be compared with the “unconstrained” LTA model in which item response probabilities are estimated at each time point. To further address sex as a biological variable, models will also be fitted by sex, with statistical comparison of results observed in boys and girls. All analyses will be performed with SAS software version 9.4 (SAS Institute) using the PROC LTA procedure.

The primary outcome will be assessed after assignment of individuals to the latent classes that they had the highest probability of belonging to (based on the posterior probability provided by the model at baseline). A straightforward analysis of the primary outcome will follow and involves comparison of the proportion of children achieving a minimally importance difference in ACQ of at least 0.5 in each of the latent classes via a Chi-Square test.

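### As written, Aim 1 cannot tell a poorest-in-all-domains symptom cluster from the top slice of a single overall-severity continuum

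*Combined protocol and SAP*

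**What the plan says.** Section B, Aim 1, states two hypotheses: that "A cluster of children with the poorest physical, mental, and social health symptoms will be identified by latent class analysis", and that "this cluster will have stable symptom presentations over time". Section A describes symptom clusters as "defined as two or more concurrent symptoms independent of other clusters".

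Section U (plan for aims 1-3) gives the method. "Discrete latent classes of individuals are identified based on their shared characteristics across a set of observed categorical variables", and the inputs are "patient-reported symptoms (global, mental, social and physical health categories) and measures of asthma disease activity" at four time points. "The number of classes will be statistically determined using the Bayesian information criterion"; where BICs are close, class prevalence decides, so that classes under 5% are avoided. The stability check sets a constrained model, in which "the same cluster structure is forced into multiple time points", against an unconstrained one. No non-class model, separation criterion or refuting result is named for Aim 1. Section T takes four clusters as a planning assumption.

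**The concern.** Every candidate model in the plan is a class model. The one-class model says that the indicators are unrelated, so the choice between one class and several mainly tests whether symptoms are correlated. If children differ only in overall severity, the symptoms are correlated, and a class model can absorb that only by adding classes. Those classes are mild-to-severe bands, and the top band is poorest in every domain.

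The obvious rival to the Aim 1 hypothesis is that some children are simply worse overall. Section D presents the study as the first to identify symptom clusters in this population, and section F expects physical, mental and social symptoms to act together. Severity bands would satisfy the Aim 1 wording without showing either. Aims 2 and 3 then use the class labels as predictors, so the interpretation carries forward.

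**Working it through.** **1. The plan's own figure.** Section T, Table 3: chi-square test, N=147, df=3, W=0.275, alpha 0.05. The noncentrality is N × W² = 147 × 0.275² = 11.12, which gives power 0.808, as printed. All 45 cells of Table 3 reproduce within 0.001. They are conditional on clusters existing, so they do not bear on this point.

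**2. Inputs.** N=147 is the section T figure after 15% attrition. Counting four PROMIS categories plus ACQ, ACT, lung function, exhaled nitric oxide and blood eosinophils gives 4 + 5 = 9 indicators. Counting the 13 short forms in section L instead gives 13 + 5 = 18. Loadings, cut-points and trait stability are assumptions. With equal loadings a, the correlation between two underlying scales is a²: 0.09, 0.16, 0.25 and 0.36 at a = 0.3, 0.4, 0.5 and 0.6.

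**3. The rule.** BIC = −2 log L + p ln N, with ln 147 = 4.990. For K classes and J binary indicators, p = (K−1) + KJ. Going from one class to two adds J + 1 parameters, a penalty of 10 × 4.990 = 49.9 for J=9 or 19 × 4.990 = 94.8 for J=18. The rule counts as met when BIC picks at least two classes and one class is worst in the physical, mental and social domains.

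**4. How often the rule is met when no clusters exist (N=147).**

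| Simulated truth | Indicators | Rule met |
|---|---|---|
| One factor, one wave, all indicators at the loading | 9 | 38% at 0.4; 98-99% at 0.5; 100% at 0.6 and 0.7 |
| One factor, one wave, lung function, nitric oxide and eosinophils at 0.1 | 18 | 22-50% at 0.4; 99.5% at 0.5; 100% at 0.6 |
| Same | 9 | 2.5% at 0.4; 44% at 0.5; 96.5% at 0.6; 100% at 0.7 |
| One factor, four-wave transition model | 18 | 100% at 0.3-0.6 |
| Same | 9 | 0% at 0.2; 54% at 0.3; 100% at 0.4-0.6 |
| Three domain factors, r=0.5, loading 0.6 | 9 and 18 | 95-100% |
| Three domain factors, r=0.5, loading 0.8 | 9; 18 | 65%; 52% |
| Three domain factors, r=0.3, loading 0.7 | 9; 18 | 85%; 38% |
| Three domain factors, r=0.3, loading 0.8 | 9; 18 | 32%; 13% |
| Three domain factors, r=0 | 9 | 17% (two or more classes in 85%) |
| Independent indicators | 9 | 0% |

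Cells rest on 40-200 runs. With 40 of 40 runs positive, a miss rate up to about 3/40 = 7.5% is not excluded. Smaller cohorts (N=80-100, 18 indicators) gave 85-87% at loading 0.5 and 100% at 0.6. In the one-factor single-wave runs, class profiles were ordered by severity and did not cross.

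**5. The stability half.** In the four-wave runs the continuous trait was set 70% stable between waves. The poorest class then had a median probability of staying put of 0.67-0.91. Stability therefore gives little protection against the continuum explanation.

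**6. What a one-factor comparator adds.** A one-factor model has 2J parameters: 18 against 19 for two classes (J=9), or 36 against 37 (J=18). When the truth was one factor at loadings 0.5-0.7, the class model had the lower BIC in only 0-10% of runs. With two real classes and 18 indicators, the one-factor model won in 0% (item rates 0.70 vs 0.15) and 6% (0.60 vs 0.20). The plan's rule chose at least two classes in 100% of runs under both truths.

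**7. What it cannot do.** Three true classes ordered by severity (item rates 0.75/0.45/0.15) beat the one-factor model in only 10% of runs (9 items) and 2% (18 items), and in no more than 31% in a repeat. With three continuous domain factors and no clusters, classes beat one factor in 47% (9 items) and 67% (18 items) at loading 0.8, r=0.3. Requiring classes also to beat a three-factor model rejected genuine crossing clusters in 98-100%.

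**The case against.** The strongest reply has three parts.

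- The hypothesis is not empty. If physical, mental and social burden fall on different children, no class is worst in all three domains. The rows with weakly correlated domains, or with strong within-domain loadings, show this. This stands. A reader might infer that Aim 1 can fail only if symptoms are uncorrelated, or that it succeeds almost always whenever clusters are absent. Neither follows: the high rates need a near-single severity scale.
- A comparator used as a gate on whether clusters exist would be unreliable in both directions (step 7). This also stands, and it limits the fix to reporting and wording.
- The primary analysis compares the proportion with an ACQ reduction of at least 0.5 across assigned classes, and that question can be answered whether the classes are discrete or bands. This stands too. A reader might infer that Aims 2 and 3 are invalid; the documents do not support that.

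A further tempting reading is that the rule is met more often without clusters than with them. One simulated set of four genuine clusters met it in only 30% of runs, but that depends on invented class profiles and carries no general weight.

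None of this supplies what is missing: section U contains no model under which children differ only in degree.

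**Conclusion.** The point holds in a limited form. Under a single severity scale with at least moderate correlation (assumed loadings of about 0.5 or more across all of 9 to 18 indicators in one wave, or about 0.3-0.4 and above in the four-wave model), the Aim 1 prediction is met in about 98-100% of simulated cohorts that contain no clusters. Three weakly related measures among nine cut this to 44% at loading 0.5, and separate domain factors can bring it much lower. The simulations left out missing data, covariates and the unknown split between Options 1 and 2.

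What is affected is the inference that distinct symptom clusters exist. The class assignment remains usable as a descriptive grouping. This is a worthwhile, inexpensive change and does not overturn the primary analysis.

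**What to change.** In section U, plan for aims 1-3:

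- Fit a one-factor (continuous-severity) latent trait model to the same baseline indicators. Report its BIC beside that of the selected class model, and report whether class profiles cross or are strictly ordered.
- If the one-factor model fits as well or better, or the classes are strictly ordered, describe them as severity bands that the data do not distinguish from a continuum.
- If the class model fits better, conclude only that a single severity scale is inadequate, and show a correlated three-domain factor model as a further sensitivity comparison. Do not treat either result as proof for or against discrete clusters.
- Keep class assignment as the planned predictor in Aims 2 and 3, and add the continuous severity score as a sensitivity predictor.

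In section B, reword the Aim 1 hypothesis so that it predicts a class structure not explained by overall severity alone.

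The cost is a little extra modelling on data already being collected and a few sentences of text, and Aim 1 may end up supporting a weaker statement. Section V places the outcome analyses in Year 5, so the change can be specified beforehand if they have not begun.

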### **Aim 2. Determine associations between symptom clusters and clinical outcomes in children with exacerbation-prone asthma.**

Hypotheses: Children with the poorest physical, mental, and social health symptoms will have the poorest corticosteroid treatment responsiveness and quality of life.

### **Aim 3. Identify inflammatory and metabolic pathways underlying symptom clusters in children with exacerbation-prone asthma.**

Hypotheses: Symptom clusters will be distinguished by systemic and airway inflammatory cytokine profiles and metabolomic biomarkers.

[name] is also receiving supplemental funding to pursue two additional aims related to climate change. Climate change poses a significant threat to respiratory health in patients with asthma. The effects are direct, through extreme heat or humidity, and indirect, through

synergistic disturbances in air quality and airborne allergens. For example, rising temperatures accelerate production of pollutants such as ozone, fine particulate matter (PM2.5), polycyclic aromatic hydrocarbons, and volatile compounds, which alter airway function and host defense through epigenetic modifications in immune cells, airway eosinophil infiltration and epithelial inflammation. Heavy metals, nitrates and sulfur pollutants can also agglomerate on the surface of pollen grains and may increase allergenic potential and absorption of these toxicants once inhaled.

The effects of climate change and air pollution are not equal. **Children are more susceptible.** Children have a higher respiratory rate and minute ventilation, which increases pollutant inhalation, and more narrow airways, which amplify particulate trapping, absorption, and epithelial inflammation and oxidative stress. The negative effects of climate are increased further in **socially vulnerable populations**. Black and Hispanic children are more likely to live in lower opportunity neighborhoods due to systemic structural racism and historic red lining practices, are exposed to more pollutants, and have more severe asthma exacerbations attributable to air pollution. They are also projected to have a 1.3-fold risk of living in a neighborhood with the highest projected increases in asthma due to increased PM concentrations. In these neighborhoods, fears about crime and safety and limited recreational green space also force children indoors. However, poorer housing standards allow for increased infiltration of outdoor pollutants into the home. Impaired ventilation or filtration also results in 2-5 higher pollutant concentrations when compared to what is experienced outdoors.

Through supplemental funding, the study team will also test the central hypothesis that climate change-induced disruptions in air quality worsen asthma inflammation, symptoms, and longitudinal outcomes in school-age children with asthma and that these effects are mediated by social vulnerability. Two additional aims to be pursued are below:

**Aim 4. Determine associations between climate, air quality, symptoms, and outcomes in children with exacerbation-prone asthma during two climate seasons.**

Hypothesis: Children with greatest social vulnerability will have more air pollution exposure, increased symptoms, poorer lung function, more exacerbations and decreased QOL during each season.

**Aim 5. Determine the biological impact of climate and pollutants in children with exacerbation prone asthma.** Children with greatest social vulnerability and the highest air pollution exposure will have differentially expressed cytokines and metabolomic features.

This project involves a multidisciplinary team with a history of collaboration and is aligned with the NINR Strategic Plan to “*Advance Symptom Science Research*” in chronic conditions through biobehavioral research. The study population, children with exacerbation-prone asthma, has also been understudied in this regard. This project is expected to: 1) refine knowledge regarding the identification and clinical utility of symptom clusters in these children, and 2) identify mechanisms underlying symptom clusters that can be targeted in future interventional studies, to reduce the high morbidity and improve quality of life.

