### **Plan for supplemental R01 funding (aims 4-5)**

Aim 4 will determine associations between neighborhood air quality indices (predictor variables) and patient-reported asthma control and symptoms, lung function, exacerbation rates and QOL (outcome variables) during two separate seasons (spring/summer versus fall/winter) in children stratified by high- versus low-to-moderate social vulnerability. Prespecified outcomes are continuous and will be evaluated with linear regression. Analyses will be stratified by social

vulnerability (high versus low-to-intermediate) and season (spring/summer versus fall/winter). Models will be generated for air quality variables on the visit date and for each of the five lag days prior to the visit. Given the relatively small number of participants and high number of air quality predictor variables, we will use ElasticNet to select the most important variables in Python. Variables with a Pearson correlation coefficient  $>0.8$  will be removed to minimize redundancy. Models will be evaluated considering pertinent covariates such as age, asthma medications and tobacco smoke exposure. To further address sex as a biological variable, models will also be fitted by sex, with statistical comparison of results observed in boys and girls. Analyses will assume a type 1 error rate of 0.05 without adjustments for multiple testing (exploratory study). For exploratory dichotomized outcomes that are not pre-specified, such as exacerbation occurrence or QOL scores below a threshold, partial least squares regression and discriminant analysis could be performed to determine the air quality features that provide the largest separation between outcomes. Temporal stability of the results would be assessed by repeating analyses during the second season.

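### Aim 4 names climate as an exposure, but its planned models contain only air quality predictors, so no climate association is estimated and temperature has no planned adjustment within each half-year season

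*Combined protocol and SAP*

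**What the plan says.** Section B states Aim 4 as "Determine associations between climate, air quality, symptoms, and outcomes in children with exacerbation-prone asthma during two climate seasons". Climate and air quality are separate items in that list. The rationale just before it says of climate change: "The effects are direct, through extreme heat or humidity, and indirect, through" disturbed air quality and airborne allergens. It adds that "rising temperatures accelerate production of pollutants such as ozone" and fine particulate matter. The central hypothesis of the supplement is that "climate change-induced disruptions in air quality worsen asthma inflammation, symptoms, and longitudinal outcomes in school-age children with asthma".

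Section U (plan for aims 4-5) turns this into models. "Aim 4 will determine associations between neighborhood air quality indices (predictor variables) and patient-reported asthma control and symptoms", along with lung function, exacerbation rates and quality of life. On timing: "Models will be generated for air quality variables on the visit date and for each of the five lag days prior to the visit". ElasticNet is brought in because there are many air quality predictors, and one of any pair correlated above 0.8 is to be dropped. On adjustment: "Models will be evaluated considering pertinent covariates such as age, asthma medications and tobacco smoke exposure". Models are stratified by social vulnerability and by two half-year seasons, and tested at 0.05 without multiplicity adjustment as an exploratory study.

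No temperature, humidity or pollen variable, data source or model term appears in the outcomes (Section J), the procedures (Sections K and L), the analysis plan (Section U) or the schedule (Appendix I).

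**The concern.** There are two separate problems.

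First, the aim lists climate as something to be related to symptoms and outcomes, but no planned model contains a climate term. Season defines which children-visits go into which model. It has no coefficient, and a comparison of two half-year strata does not estimate an association with heat or humidity.

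Second, the rationale describes temperature as acting directly on asthma and also as raising pollutant levels. A variable that causes both exposure and outcome is a confounder of the exposure-outcome association. If it is left out, a pollutant coefficient carries part of the effect of that day's heat, and a pollutant with no effect can be reported as harmful. An attribution to air quality, as distinct from the weather that came with it, would then not be supported.

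**Working it through.** **Aim against plan**

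| Item | Section B | Section U, Aim 4 |
|---|---|---|
| Climate | Named as an item of the aim | Two half-year strata, no term |
| Air quality | Named | Only named predictor, visit day plus five lag days, ElasticNet pool |
| Temperature | Direct effect; raises pollutants | Not named |
| Humidity | Direct effect; not said to raise pollutants | Not named |
| Airborne allergens | Indirect route; not said to raise pollutants | Not named |

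Only temperature has both arrows in the protocol's text, so the confounding argument rests on temperature alone.

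**What stratification leaves**

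Fitting spring/summer and fall/winter separately removes weather differences between the two half-years. Each half-year still spans cool and hot days. The visit-day and lag-day models draw on exactly that remaining day-to-day variation.

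**Size, by an omitted-variable calculation**

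The plan gives no sample size or power for Aim 4, so there is no stated figure to reproduce. Inputs:

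- From Section T: 173 enrolled, 147 after 15% attrition.
- Assumed cell sizes: 147/4 ≈ 37 (two vulnerability groups by two seasons, each child counted once), or 173/2 ≈ 87 (every enrolled child contributes to both seasons). Both assume even splits.
- Assumed, not in the documents: within-season correlation r between pollutant and temperature, and the share R² of outcome variance that temperature explains.
- True pollutant effect: zero.

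The spurious pollutant-outcome correlation is s = r × √R². By Fisher's z, d = atanh(s) × √(n − 3), and the rejection rate at two-sided 0.05 is Φ(d − 1.96) + Φ(−d − 1.96).

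Worked case, r = 0.5, R² = 0.05, n = 37: s = 0.5 × 0.224 = 0.112; d = 0.1123 × 5.831 = 0.655; rejection = 10.0%.

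| r | R² | s | n = 37 | n = 87 |
|---|---|---|---|---|
| 0.3 | 0.03 | 0.052 | 6.1% | 7.6% |
| 0.5 | 0.05 | 0.112 | 10.0% | 17.7% |
| 0.5 | 0.10 | 0.158 | 15.3% | 30.9% |
| 0.7 | 0.05 | 0.157 | 15.1% | 30.4% |
| 0.7 | 0.10 | 0.221 | 25.9% | 54.1% |

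A simulation of the same set-up at n = 87 (20,000 replicates) agrees: 17.7% to 54.4% over the last four rows without temperature. With temperature in the model, rejection is back at about 5% (4.8% to 5.3%).

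The calculation tests one pollutant at a time. It does not represent ElasticNet selection among many.

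**The case against.** The strongest reply is that the supplement is really about air quality. The central hypothesis concerns air quality disturbed by climate change, and Aim 4's own hypothesis concerns air pollution exposure by social vulnerability. Air quality predictors fit both. This stands, and it is why rewording the aim is an acceptable remedy. It does not settle the confounding, because attributing an association to air quality still requires separating it from same-day heat.

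A second reply is that the covariate list is open and the air quality indices are not itemised, so weather is unspecified, not excluded. That is correct as far as it goes. It does not cure the gap: the stated predictor set has no climate variable, and an open list leaves the adjustment to be chosen after the data are seen.

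A third is that the size rests on chosen inputs. This stands. The larger cell of 87 is also optimistic for lung function: Option 1 has a single in-person visit, and telephone follow-up under Option 2 omits spirometry (Section K).

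A reader might also infer that heat, humidity and pollen are all confounders by the protocol's own account. The text does not support that. Humidity is named only as a direct effect, and airborne allergens only as an indirect route; pollutants are said to settle on pollen, not to be produced by it. Nor does the text support reading the confounding as untouched, since season stratification removes the between-season part.

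**Conclusion.** The point holds in two parts. As written, Aim 4 estimates no association with climate; this follows from the text and needs no assumption. Temperature is also an unadjusted common cause of pollutant level and outcome within each half-year, on the protocol's own reasoning.

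The inflation of a nominal 5% test could be slight (about 6% in the mildest case shown) or large (10-26% at 37 per cell, 18-54% at 87). It depends wholly on the assumed correlation, variance share and cell size. The 54% figure should not be read as the expected error rate: it combines the strongest assumed inputs with every enrolled child contributing to both seasons.

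The change is worth making but not critical. Aim 4 is exploratory and the primary outcome is unaffected.

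**What to change.** In Section U, Aim 4:

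1. Add daily temperature and relative humidity, with data source, matched to the same visit date or lag day as the pollutant. Treat them as climate predictors and report their associations from models without pollutants, since pollutants lie on the pathway from climate to outcome.
2. In each pollutant model, include same-lag temperature (and humidity) as an unpenalised covariate outside ElasticNet and exempt from the 0.8 correlation rule. Report the climate-adjusted pollutant coefficients.
3. Pollen may be added as a co-exposure where records exist. A smooth calendar term is optional.

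If weather data will not be linked, reword Aim 4 as an air quality aim, and do not attribute pollutant associations to air quality independently of same-day weather.

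The cost is linkage of routine weather records, one or two degrees of freedom per model, and wider intervals where pollutant and temperature are highly correlated. No new participants or procedures are needed.
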